**AEROSOLIZED SURVANTA IN NEONATAL RESPIRATORY DISTRESS SYNDROME:
PHASE I/II STUDY (IND 115430)**

NCT02294630

FINAL STUDY PROTOCOL & STATISTICAL ANALYSIS PLAN

Date of last Revision: 07-31-2017

RESEARCH STRATEGY

1.1. Research Design:

1.1.1. Study Design:

This is a proposal for the Phase II portion of our unblinded Phase I/II trial^{1,2}. It is a safety, feasibility and dose finding study of AS for the treatment of RDS in spontaneously breathing PT neonates receiving NIV. To remove selection bias and control temporal trends, infants will be randomized to 4 parallel fixed dosing schedule groups^{1,2}. This Phase II study will identify 1 or 2 optimal doses, and provide additional data for safety, feasibility and early indication of efficacy that will be the basis for designing a definitive Phase III trial. Optimal dose(s) will be identified based on evidence of a significant positive trend with increasing dose, even if no two groups are significantly different^{3,4}. Equitable representation of GAs within each dose group will be achieved by stratified randomization. Equitable representation of two FDA-approved nebulizers will be achieved by using block sizes of 8. It is expected that choice of nebulizer device will not affect efficacy but may influence caregiver preference based on institutional practice and ease of administration (feasibility).

1.1.2. Inclusion Criteria:

1. Infants admitted to the NICU at Hutzel Women's Hospital (HWH)/Children's Hospital of Michigan (CHM)
2. Gestational age of 24^{0/7}-36^{6/7} weeks
3. Postnatal age \leq 24 hours
4. Clinical diagnosis of RDS based on (i) presence of at least two of the four classic symptoms (need of supplemental oxygen, tachypnea, intercostal retractions or grunting), *and* (ii) exclusion of other causes of respiratory failure (Section 3.6.4.1) *and* (iii) Clinician intent to administer surfactant if infant requires intubation
5. Respiratory support with NIV (CPAP or NIPPV or HFNC) with FiO₂ \geq 25% or PEEP \geq 4 cmH₂O or HFNC rate \geq 2 LPM for \leq 8 hours
6. Written informed consent from parent/guardian

1.1.3. Exclusion Criteria:

1. Previous receipt of surfactant
2. Infants with respiratory distress who are unstable and require immediate intubation (Section 3.6.5)
3. Active air leak syndrome (e.g. pneumothorax, pneumomediastinum)
4. Lethal congenital malformations; death anticipated within first 3 days of life; decision to withhold support

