Diagnosis of RDS will be based on⁵ (i) presence of at least two of four classic symptoms (need of supplemental O₂, tachypnea, intercostal retractions or grunting), *and* (ii) exclusion of other causes of respiratory failure, *and* (iii) Clinical team plan to administer surfactant if infant requires intubation. A chest x-ray (CXR) is not mandatory prior to enrollment; however, if obtained clinically, severity of RDS will be graded and results recorded (Appendix VII [Table A4])⁶. We have not mandated a radiologic diagnosis of RDS because classic radiologic findings may evolve over the first 12-24 hours and be modified by early NIV; furthermore, the need for a CXR may unnecessarily delay study intervention^{7,8}.

1.1.4.2. Timing of Aerosolized Surfactant:

Enrolled infants will receive AS at ≤ 24 hours of age & within 8 hours of initiating NIV as several studies have shown that earlier administration of surfactant to PT babies with RDS improves outcomes.

1.1.4.3. Study Intervention – Aerosolized Surfactant Preparation and Dose:

For this study, Survanta (200 mg PL/8 ml) (Beractant, Abbvie Inc.) will be used at two doses – 100 mg/kg and 200 mg/kg and two dilutions (1:1 and 1:2) resulting in 4 dose schedule groups.

Survanta has been chosen as the surfactant for this study as this is the surfactant used exclusively at our institution; it is also the most commonly used surfactant with the longest duration of use in the US^{9,10}. *We will validate aerosolized use of other surfactants in subsequent studies.* Many studies have compared Survanta with other animal derived surfactants, however, consensus regarding the best preparation has yet to be determined¹⁰. Although several relatively small randomized controlled trials (RCTs) showed significant reductions in mortality and need for redosing with high-dose (200 mg/kg) but not low-dose (100 mg/kg) poractant alfa vs. beractant (100 mg/kg)^{11,12}; three large recent retrospective cohort studies of surfactant use in the US (n=51,282 and 14,173) and Australia (n=515) published in 2013 failed to show significant differences in outcome between poractant and beractant in PT neonates with RDS^{9,13,14}. It is speculated that previously described differences in mortality between surfactants may relate to site variation in outcomes⁹.

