- ii). Secure cooperation of clinical bedside nurses and respiratory therapists in administering aerosol.
- iii). Identify and randomize a sufficient number of patients within a reasonable study period. This includes ability to identify eligible infants, obtain informed consent, and prepare and deliver aerosolized study medication in the defined time frame.

1.1.7.3. Dose Finding:

We will randomize infants to receive one of 4 fixed dosing schedules. Data collected during this Phase I/II trial will be critical in selecting the optimal dosing schedule for the definitive Phase III trial. Optimal dosing schedule will be determined by preliminary evidence of efficacy, lack of adverse effects, and tolerance by patients and bedside clinical caregivers.

1.1.7.4. Efficacy:

The primary efficacy outcome for this Phase I/II trial is the need for need for intubation and MV within 72 hours of study intervention (treatment failure). This will be compared to a historical control rate of 0.5 for need for intubation in PT infants 24-36 weeks GA undergoing NIV. Treatment failure criteria are defined *a priori* in Section 3.6.5. We chose treatment failure within 72 hours of randomization as our primary efficacy outcome as failure within that time would likely be due to RDS, whereas failure after this time would more likely be due to secondary causes like sepsis, PDA, pneumonia, NEC, IVH, or apnea of prematurity.

1.1.8. Secondary Efficacy Outcomes:

1. CBG/ABG, pulse oximetry, vital signs at 60±30 minutes after end of AS
2. Number of doses of surfactant – aerosolized & intratracheal
3. Respiratory support at 24, 48 & 72 hours, 7 days (D7), D14, D28, 36 weeks corrected GA and Discharge.
4. Pneumothorax, pneumomediastinum or other air leak
5. Changes in cerebral oxygenation as evaluated by NIRS
6. Changes in surfactant activity in gastric aspirates
7. Cumulative duration of NIV and invasive ventilation on D3, D7, D14, D28, 36 weeks CGA and discharge
8. Duration of supplemental oxygen, intensive care, hospital stay
9. Age at start of feeds, feeding progression, age at full enteral feeds
10. Need for blood transfusions
11. Growth parameters at 7 days, 28 days, 36 weeks corrected GA and discharge
12. Morbidities associated with prematurity: PDA, IVH (Grade III-IV), NEC, periventricular leukomalacia, ventriculomegaly, ROP (stage>3 or requiring treatment), and BPD. Two definitions of BPD will be used:

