	0.35	0.27	0.44	$\pm 8\%$
	0.40	0.32	0.49	$\pm 9\%$

Type I error of 0.05, two-tailed test

Sample Size Based on the Null Hypothesis & Error Rates:

We will also compare the primary efficacy outcome to that of historical controls. The eligibility criteria, baseline factors, clinical management protocols, criteria for NIV and MV, & outcomes in our study are similar to those of recently published clinical trials. The use of historic controls will decrease sample size, shorten duration, and enhance efficiency of our Phase II study; definitely an advantage for testing four dosing regimens in this orphan population^{1,90-94}. Additionally, since AS has been shown to be potentially beneficial, this will allow all patients to receive study medication early and non-invasively thus enhancing study feasibility.

The rate of intubation following NIV for RDS among 24-36 weeks GA PT infants is ~50%^{75,95}. We estimated a 50% relative risk reduction to be clinically significant and plausible based on our preliminary data & reports in literature. Studies of MIST during NIV in PT infants 24- 36 weeks GA with RDS show an absolute risk reduction of the need for MV of 10-50% and a relative risk reduction of 21-63% (RR 0.67, 95% CI 0.57, 0.79) with a lower treatment threshold (FiO₂≤0.45) conferring a greater advantage (RR 0.72, 95% CI 0.59, 0.87) compared to a higher threshold (FiO₂>0.45) (RR 0.55, 95% CI 0.40, 0.77)^{5,33,75,92,93,95-104}.

A sample size of 30 subjects within each dose schedule group will have 81.8% power to detect a relative risk reduction of 50% (absolute risk reduction 25%) in the primary outcome of the need for intubation in 72 hours compared to a historical control value of 0.5 in a two-tailed type I error rate of 0.05 (Table 13).

Collapsing dilution groups corresponding to dose of 100 mg/kg & 200 mg/kg or considering our entire sample of 120 subjects all of whom receive AS will allow us to detect a smaller effect size with greater power.

An alternative strategy for sample size of Phase II trials is to reduce the level of rigor required by increasing the Type I error rate to as large as 25%^{90,105}. This increases the risk of erroneously concluding that the treatment is worthy of further investigation but does not increase the risk of missing an efficacious treatment. This approach would allow us to evaluate the effect sizes in Table 13 with smaller sample sizes.

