Analysis plan to address Aim #2: - Determination of Optimal Dilution and Dosage of AS: The optimum dose is one that produces low toxicity while nearly maximizing the biological response⁸⁹. The optimal dosage will be determined by comparing levels of adverse responses, feasibility items and primary and secondary efficacy treatment outcomes (rates of intubation, diagnosis of PDA, need for blood transfusions, postnatal growth, duration of respiratory support, length of hospital stay, and incidence of complications of prematurity including IVH, sepsis, pneumonia, BPD, NEC, ROP, and death) across the four dosing schedules (Appendix IX, Mock Tables). The optimal dosage/dilution will be the one with the minimum level of adverse responses and highest clinical treatment outcomes.

Analysis plan to address Aim #3 - Short-term efficacy of AS: The primary outcome variable for short-term efficacy is the need for intubation & MV within 72 hours of AS. We will estimate the unconditional probability of benefit for the four dosing schedule groups (I, II, III, IV), the 2 dose groups (100 vs. 200 mg/kg) and the entire study cohort of 120 subjects. We will also compare with reported rates of intubation in historical controls (50%). A special χ^2 test to compare sample proportion with population proportion will be conducted to test the study hypothesis that AS is efficacious. In the comparison analysis, different dosages/dilutions will also be considered as weight using the “optimal” dosage/dilution obtained from Aim #2 as reference. A significantly lower rate of intubation in infants treated with AS in this study as compared to the reported rate of ~0.5 at $p < 0.05$ level (two-sided) will be used as evidence supporting the efficacy of AS. However, it is likely we may not

have power to achieve statistically significant results. Nevertheless these preliminary efficacy data will be crucial in determining outcome measures and effect size for the definitive placebo-controlled Phase III trial.

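### The efficacy test compares a 72-hour, post-entry intubation rate with a fixed 0.5 that the plan never ties to the same entry point or time window

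*Combined protocol and SAP*

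**What the plan says.** **The trial's rate.** Section 1.1.7.4 defines the primary efficacy outcome as the "need for intubation and MV within 72 hours of study intervention (treatment failure"). It justifies the cut-off by saying that "failure after this time would more likely be due to secondary causes like sepsis, PDA, pneumonia, NEC, IVH, or apnea of prematurity". Later failures are therefore expected and deliberately not counted. AS is given "within 8 hours of initiating NIV" (section 1.1.4.2; the same limit is in inclusion criterion 5). Exclusion criterion 2 in section 1.1.3 removes "Infants with respiratory distress who are unstable and require immediate intubation".

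**The comparator.** Section 1.1.7.4 says: "This will be compared to a historical control rate of 0.5 for need for intubation in PT infants 24-36 weeks GA undergoing NIV". Section 1.1.10 says: "The rate of intubation following NIV for RDS among 24-36 weeks GA PT infants is ~50" per cent, citing two published studies, and sets the 72-hour outcome against that value in the power statement. Section 1.1.12 calls it the reported rate in historical controls. None of the three places gives a starting point, an entry condition or a length of follow-up.

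**The rule.** Section 1.1.12, Aim #3: "A significantly lower rate of intubation in infants treated with AS in this study as compared to the reported rate of ~0.5 at" the two-sided 0.05 level is to count as evidence supporting efficacy.

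**Related provisions.** Section 1.1.5 plans own-unit controls, to compare intubation rates in enrolled and non-enrolled infants. The data monitoring committee (DMC) items at the end of section 1.1.12 ask for outside intubation rates by gestational-age stratum, a curve of intubation timing, and a primary intention-to-treat analysis of all enrolled infants. None of these changes the value that Aim #3 tests against.

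**The concern.** A one-sample test against a fixed value is only as good as that value. The 0.5 has to be the rate that the same kind of infant, at the same point in the course of NIV and over the same 72 hours, would have had without AS. The plan does not show that it is.

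If the published rate counts from the start of NIV, it includes early failures that trial entry removes. If it runs beyond 72 hours, it includes the later failures that section 1.1.7.4 sets aside. Either would place the no-AS rate in the trial's own window below 0.5, and the rule could then be met with no AS effect. Aim #3 also says these data will inform the effect size for Phase III, so an inflated difference would be carried forward.

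This point is about the time window only. It does not concern gestational-age mix or the sampling error of the published rate.

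**Working it through.** **1. The plan's own figures reproduce.** Table 13 is matched by the arcsine power formula, Φ(2·|arcsin√0.5 − arcsin√p|·√n − 1.96):
- n = 30, p = 0.25: 2 × (0.7854 − 0.5236) × 5.477 − 1.96 = 0.908, giving 81.8% (plan 81.8%).
- n = 60: 98.2% at 0.25 and 89.0% at 0.30 (plan the same).
- n = 120: 99.99%, 99.5% and 91.6% at 0.25, 0.30 and 0.35 (plan 99.9%, 99.5%, 91.6%).

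The power arithmetic is sound. The open question is the null value.

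**2. When the rule fires.** Significance below 0.5 requires (x − n/2)/√(n/4) ≤ −1.96:
- n = 30: x ≤ 15 − 1.96 × 2.739 = 9.63, so 9 or fewer.
- n = 120: x ≤ 60 − 1.96 × 5.477 = 49.3, so 49 or fewer.
- n = 200: x ≤ 100 − 1.96 × 7.071 = 86.1, so 86 or fewer.

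Section 1.1.12 names a cohort of 120. The 200 is the enlarged Phase II total of 220 in section 1.1.10 less the 20 allowed for screen failures.

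**3. Chance of declaring efficacy with no AS effect.** This is the exact binomial probability of a count at or below those limits. The true in-window rate is an assumption, because the documents do not give it.

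| True no-AS rate, entry to 72 h | n = 30 (one schedule) | n = 120 | n = 200 |
|---|---|---|---|
| 0.55 | 0.5% | 0.1% | <0.1% |
| 0.50 | 2.1% | 2.7% | 2.8% |
| 0.45 | 6.9% | 20% | 31% |
| 0.42 | 12% | 44% | 64% |
| 0.40 | 18% | 61% | 83% |
| 0.35 | 36% | 92% | 99% |

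The chance passes 50% at a rate of about 0.32 for n = 30, 0.41 for n = 120 and 0.43 for n = 200. At 0.40, the chance that at least one of four schedules fires is 1 − (1 − 0.176)⁴ = 54%. With an exact binomial test in place of χ², the n = 120 figures are slightly lower: 16%, 36% and 54% at 0.45, 0.42 and 0.40.

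**4. What mismatch would give those rates.** Let a be the proportion of comparator infants intubated before an entry-equivalent time, and b the proportion first intubated after 72 hours. The matched rate is (0.5 − a − b)/(1 − a). At n = 120:
- a = 5%, b = 0: 0.45/0.95 = 0.474; fires 9%.
- a = 0, b = 5%: 0.45; fires 20%.
- a = 10%, b = 0: 0.40/0.90 = 0.444; fires 24%.
- a = 5%, b = 5%: 0.40/0.95 = 0.421; fires 43%.
- a = 0, b = 10%: 0.40; fires 61%.

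To reach about 0.4125, late failures alone would need b = 0.0875, which is 0.0875/0.5 = 17.5% of comparator intubations. Early failures alone would need a = 0.0875/0.5875 = 0.149, about 30% of them.

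**5. How far a significant result depends on the null.** With the score test, significance is lost once the null falls to the upper 95% score limit. For n = 120 these limits, as printed in Table 12, are 0.44 for an observed rate of 0.35 and 0.49 for an observed rate of 0.40. An observed 0.40 is significant against 0.50 but not against 0.48.

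**The case against.** A reader might infer that the 0.5 runs earlier and longer than the trial's window, so that the bias must favour AS and the rule would fire more often than not with an inert aerosol. The documents do not support that.

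- **An unstated window is not a different window.** The titles of the two studies cited for the figure (references 75 and 95) describe randomized trials, one in infants of 29 to 35 weeks and one in mild to moderate RDS. Infants in such trials also had to reach a randomization point, and follow-up may have been fixed. If so, the mismatch shrinks or disappears.
- **The direction is open.** A comparator counted over less than 72 hours would put the null too low and work against AS.
- **Not all early failures are lost.** Infants who enrol and then meet intubation criteria before AS leave the study (section 1.1.4.9), but the DMC's primary analysis keeps them. Only failures before enrolment are missing.
- **Modest mismatches mostly fire below 50%.** This is visible in step 4, and the plan's sample-size basis of 30 per schedule is much less sensitive.
- **The plan is cautious.** It says the trial is not powered for efficacy and calls the efficacy data preliminary. It also asserts that eligibility, management and outcomes resemble those of published trials.

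The first four points stand, and they make the conclusion conditional. The last does not remove it. The similarity statement gives no entry point or window for the 0.5, the own-unit controls are not the value tested, and low power does not protect against a null set too high.

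**Conclusion.** The concern holds in conditional form. Aim #3 treats p < 0.05 against about 0.5 as evidence of efficacy, and the documents never show that 0.5 is a rate from an equivalent entry point to 72 hours. Until they do, a significantly lower rate cannot be attributed to AS.

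The size depends on an unknown. The pooled test of 120 has a false-efficacy chance of about 20%, 44% or 61% if the true in-window rate is 0.45, 0.42 or 0.40. It is more likely than not to fire only at about 0.41 or below. For a single schedule of 30 the chance at 0.40 is 18%, and it passes 50% only at about 0.32 or below. The larger pooled sample now allowed raises these chances if the null is too high.

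These figures assume no AS effect, independent infants and the one-sample χ² test. They do not show that the bias exists or that it favours AS; the timing behind the 0.5 would decide that.

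**What to change.** - Do not use p < 0.05 against 0.5 as evidence of efficacy unless the SAP documents that the 0.5 is a rate from an equivalent entry point to 72 hours.
- Otherwise take the null from the non-enrolled own-unit infants of section 1.1.5 who meet the eligibility criteria and are still on NIV and not intubated at an entry-equivalent time, counted to 72 hours from that time. Give this rate with its own confidence interval, since it is an estimate.
- Use the all-enrolled intention-to-treat set for the AS rate. State one origin for the 72 hours: section 1.1.7.4 uses both intervention and randomization, and infants who exit before AS have no intervention time.
- Report the 72-hour rate with its confidence interval. Show the test over a range of null values, for example 0.35 to 0.55 so that both directions are covered, and give the value at which significance is lost.

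Extending AS follow-up to day 28 or discharge is not a good alternative. The comparator's follow-up is unknown, and this would bring in the non-RDS failures that section 1.1.7.4 leaves out on purpose.

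The cost is SAP wording and some re-tabulation, including intubation times for the own-unit controls. The apparent effect will probably be smaller. Non-enrolled infants may also differ from enrolled ones in other ways, which this change does not address.
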